17 INFORMED CONSENT PROCESS

A patient information form including the informed consent form has been prepared by the Project Manager. The content of this document needs to be reviewed and approved by the ethics committee, and suggested changes need to be implemented.

17.1 General considerations

The informed consent procedure is performed by the Principal Investigator or any investigator designated for this task as recorded in the delegation of duties log. The investigator has to fully inform the patient of all pertinent aspects of the clinical investigation in language and terms she/he is able to understand. When the patient agrees in the study participation, the patient as well as the investigator who performed the informed consent discussion both personally write the date and sign on the informed consent form. Date of the informed consent discussion as well as date of patient's signature of the informed consent form should be documented in patient's medical record. If the implantation is performed on the same day, also the time of patient's signature has to be documented. A copy of the signed and dated written informed consent form is provided to the patient.

By signing the informed consent form, the patient is included in the study. Only after that procedure any study specific procedure is performed. Pre-screening of the patient chart in respect to the inclusion and exclusion criteria is not a study specific procedure.

If during the course of the clinical investigation new information emerges, the investigator informs the patient accordingly. If this information concerns safety aspects or other aspects that could influence the decision of the patient to continue participating in the study, the patient shall be informed immediately.

17.2 Special circumstances for informed consent

Inclusion of subjects unable to read or write:

Informed consent will be obtained through a supervised oral process if a subject is unable to read or write. An independent witness will be present throughout the process. The written informed consent form and any other information will be read aloud and explained to the prospective subject and, whenever possible, either will sign and personally date the informed consent form. The independent witness also signs and personally dates the informed consent form attesting that the information was accurately explained and that informed consent was freely given.

18 ADVERSE EVENTS AND DEVICE DEFICIENCIES

In the course of the clinical investigation, undesired medical events can occur in participating patients, which are called adverse events (AEs) in the following. Furthermore, device deficiencies (DD) may also be observed. All AEs with exception of those listed in section 18.1 and all DDs of the investigational devices shall be assessed by the investigator and shall be documented and reported throughout the clinical investigation within the timelines defined below.

The investigator shall document all events on the respective CRF pages provided within the EDC system. The indicated timelines for reporting of initial cases and possible update reports shall be strictly followed.

According to ISO 14155:2011 events will be classified on the basis of the definitions below.

18.1 Definition of adverse events

An AE is defined* as any untoward medical occurrence, unintended disease or injury, or untoward clinical signs (including abnormal laboratory findings) in subjects, users or other persons whether or not related to the investigational medical device. This includes, but is not limited to:

- Events related to the investigational medical device or the comparator
- Events related to the procedures involved
- For users or other persons, this definition is restricted to events related to the investigational medical devices.

*see ISO14155:2011 3.2

Exceptions:

Phrenic nerve stimulation occurring during implantation or MPP tests are only considered Adverse Events and have to be reported in case it results in a serious medical condition.

Tachyarrhythmia episodes in a patient with ICD /CRT-D indication are not considered as Adverse Events as they are part of his underlying condition. However, tachyarrhythmia episode have to be reported as Adverse Event in case the episode resulted in a serious medical condition.

Recurrent inappropriate therapies resulting from the same origin and detected within a 3 months' time period may be summarized in one Adverse Event Report.

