18.7 Anticipated adverse events

The following Adverse Events may possibly occur as medical complications of an ICD or CRT system implantation. The most common adverse events related to the ICD or CRT therapy are listed in Tables 8a-e. All references used for this chapter refer to the list at the end of this section.

Tab.8a: Expected peri-operative events based on literature research

Frequency	Percentage (%)	Risk
Very frequent >1 out of 10 patients	7-19 ⁴⁵	LV lead exchange due to unsuccessful positioning
	3-27 ³²	Atelectasis (when thoracotomy necessary)
	3-27 ³²	Pleural effusion (when thoracotomy necessary)
	3-27 ³²	Pneumonia (when thoracotomy necessary)
	Up to 17 ³²	VT/VF exacerbation ^{8,32}
Frequent 1 to 10 patients out of 100	1-7 ³²	Infection (general)
	5.2 ^{55,56} - 6 ³²	Lead perforation
	3-4 ³²	Pericarditis (when patch lead placement necessary)
	Up to 3 ³²	Embolism
	Up to 3 ⁴⁹	Phrenic nerve stimulation
	0.6 - 2.0 ⁴⁹	Infection requiring reoperation

FOR-137-014-C / SOP-137-020.020 / CRQ-14-01202

	0.07* -3 ^{32,54}	Pericardial tamponade (2-3% during patch lead placement)
	0.93 ³¹ -10.6 ^{2,49}	Lead dislodgement
	0.12 ³¹ -3.4 ⁴⁹	Coronary sinus dissection
	0.42 ³¹ -1.1 ⁶⁸	Pneumothorax
	1.2 ⁶⁸	Hematoma
Occasionally 1 to 10 patients out of 1.000	0.7 ⁵⁴	Loosening of set screw
	0.02 ³¹ -1 ³⁰	Myocardial infarction
	0.06 ³¹ -2 ³²	Cerebrovascular accident, stroke (1-2% during thoracotomy)
	0.6 ³⁰	Lead dysfunction
	0.5 ³⁰ - 0.7 ⁵⁷	Mortality
	0.5 ³⁰	Severe pocket hematoma
	0.5 ⁵⁴	Pericardial tamponade (2-3% during patch lead placement)
	0.3 ³¹ - 0.4 ⁴⁹	Cardiac arrest
	0.2 ³⁰	Arrhythmia
	0.2 - 0.3 ⁴⁹	Respiratory arrest
	0.2 ⁴⁹	Tamponade
	0.1 - 0.4 ⁵¹	Allergic reaction to ionic contrast material
	0.14 ⁵⁰	Air embolism
	0.1 ⁴⁹	Lead fracture/ insulation failure
0.1 ⁵⁹	Ventricular fibrillation	
Rare 1 to 10 patients out of 10.000	0.09 ³¹	Drug reaction
	0.08 ³¹	Hemothorax
	0.07 ³¹	Cardiac perforation
	0.04 ³¹	Phlebitis, superficial
	0.03 ³¹	Conduction block
	0.03 ³¹	Infection related to device
	0.03 ³¹	Peripheral embolus
	0.02 ⁵² - 0.04 ⁵³	Allergic reaction to non-ionic contrast material
	0.02 ³¹	Phlebitis, deep
	0.02 ³¹	Transient ischemic attack
Very rare <1 patient out of 10.000	<0.01 ³¹	Cardiac valve injury
	<0.01 ³¹	Peripheral nerve injury
	<0.01 ³¹	AV-fistula
Not known		Allergic reaction to dexamethasone acetate, bleeding ³² , brachial plexus injury ³² , device migration ^{30,41} ,

FOR-137-014-C / SOP-137-020.020 / CRQ-14-01202

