
Frequency not assessable on the basis of the available data
		
diaphragmatic stimulation³², discomfort, erosion, exit block³², failure to insulate set screw³², hemoptysis³², injury to vagus nerve³², lead malpositioning³², lead micro-dislodgement³², local tissue reaction³⁰, muscle stimulation³⁰, nerve stimulation (general)³⁰, myocardial lesion³⁰, pocket seroma³², subclavian artery puncture³², higher x-ray load due to extended fluoroscopy times³⁴, failing of shock test⁴⁰, injury due to implantation accessories^{42,44}

--	--	--

Tab. 8b: Expected post-operative events based on literature research

Frequency	Percentage (%)	Risk
	9.7 ²⁰ - 37 ²³	Lead failure ^{20,22,23}

Very frequent >1 out of 10 patients
	2.9 ⁷ - 25.4 ²⁴	Inappropriate shocks ^{7,24,25,54}
	Up to 13 ²⁹	Device explantation (manufacturers` advisory: 4% ²⁹ , electronic failure: 2% ²⁹ , housing defects: 1% ²⁹)
	0.3 ¹ - 13.6 ⁴	Phrenic nerve stimulation
	12 ^{6,21}	Lead dysfunction
	1.2 ¹⁹ - 10.6 ²	Lead dislodgement

Frequent 1 to 10 patients out of 100
	1.7 ² - 9.5 ²	Formation of clinical significant hematomas
	7.6 ¹⁵ - 9.5 ¹	Hematoma ^{1,3,15,16,17}
	7 ⁴⁶	Subclavian vein occlusion ≥ 75%
	0.1 ⁵ - 7 ¹	Infections ^{1,5,14} (CRT-D related: 1.9 ^{1,4,13} - 1.9% ^{1,4} ; in-hospital infections: 0.7% ¹² ; infections after replacement: 1.9% ¹³)
	0.1 - 4.2 ⁶⁰	Lead fracture
	1.6 ⁷ - 3.9 ⁴	Elevated pacing threshold/ loss of capture/ failure to capture
	2.4 ³⁰	Aggregate perforation
	3.4 ³⁰	Pocket erosion
	0 ² - 1.5 ⁷	Mortality within 30 days after implant (0.4% related to implant procedure ⁷)
	1.5 ³⁰	Premature depletion of battery
	1.4 ⁷	Diaphragmatic muscular stimulation
	0.3 ² - 1.3 ⁵	Lead perforation
	1.3 ¹	Pericarditis requiring anti-inflammatory agents
	0.05 ⁷ - 1,2 ^{12,57,61}	Pneumothorax
	0.9 ¹	High LV threshold
0.7 ⁵	Oversensing	
0.6 ⁷	Discomfort	
0.6 ⁷	Pain at device pocket	

FOR-137-014-C / SOP-137-020.020 / CRQ-14-01202

	0.6 ¹	Pericardial effusion requiring intervention
	0.6 ⁷	Seroma
	0.6 ⁷	Shoulder pain
	0.5 ⁴	Lead conductor fracture
	0.5 ³⁰	M. pectoralis tremor
	0.3 ⁵ – 0.5 ¹⁸	Post-operative perforation
	0.7 ⁵⁴	Thrombosis of brachial, subclavian or jugular veins
	0.3 ¹²	Acute renal failure requiring hemodialysis
	0.3 ¹	Ipsilateral venous thrombosis
	0.3 ⁷	System- or lead-related arrhythmia
	0.2 ⁴	Elevated lead impedance
	0.2 ⁶³	Site pain
	0.2 ⁵⁴	Thrombosis of deep femoral vein
Rare 1 to 10 patients out of 10.000	0.09 ³⁵	Fluid accumulation due to heart perforation

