17.2. Variables

CIP chapter 8.3.2.1.1 Percentage of patients with successful fast ventricular arrhythmia conversion by ATP one-shot at 6-month follow-up

This endpoint examines the percentage of patients with successful conversion of ventricular arrhythmia detected in the VF zone by ATP one-shot of all patients with such episodes. Events will only be included in the analysis of this endpoint if

- 1) the arrhythmia was detected in the VF detection zone, and*
- 2) if it was classified as true ventricular tachyarrhythmia by the investigator, and*
- 3) if ATP one-shot was delivered with the recommended programming (8 pulses with 88% R-S1).*

The period under observation starts with the implantation and lasts until the 6-month follow-up. The parameter of interest Conversion_{R-S1 88%} is defined as following:

*Conversion_{R-S1 88%} = (Number of patients with at least one successful conversion / Number of patients with events as defined here) * 100%.*

Thereby, a patient is considered to have experienced successful conversion if at least one episode detected in the VF zone in that patient was converted by ATP one-shot therapies at the recommended programming, i.e ATP one-shot was beneficial and shock delivery could be avoided.

It is possible that ATP one-shot is programmed but not delivered, if the device classifies the rhythm instable. This endpoint will only investigate episodes with delivered ATP one-shot therapy.

Data file, list of episodes, identifier reocerd_ID	Descriptive	Variable name	Variable label	Variable level	Nominal values
tachyarrhythmia_episode	No	patient_display_id_full	Patient Display ID	nominal	n.a.
tachyarrhythmia_episode	No	tac_detect_zone	Detection zone	nominal	nsVT / nsT SVT VT1 / VT2 VF
tachyarrhythmia_episode	No	tac_assessment	Episode assessment	nominal	non-sustained VT / VF sustained VT / VF SVT / oversensing / other
tachyarrhythmia_episode	No	tac_vf_atp_prog	ATP one-shot programming	nominal	8 pulses with RS1 88% Other programming
tachyarrhythmia_episode	No	tac_vf_first_therapy	First therapy attempt	nominal	ATP one-shot Shock
tachyarrhythmia_episode	Yes #	tac_vf_atp_success	ATP one-shot successfully terminated the episode	nominal	Yes / No
dummy	Yes	relevant_secEP_Ilivia_SAR ⁷⁴	Episode relevant for secondary endpoint Ilivia	nominal	Yes / No

Data file, identifier patient_display_id_full	Descriptive	Variable name	Variable label	Variable level	Nominal values

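### Protocol 18.1 exempts non-serious tachyarrhythmias from adverse-event reporting whatever their cause, so episodes provoked by the device, its therapy, pacing or the lead get no causality rating

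*Protocol*

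**What the plan says.** Protocol 18.1 opens with a broad AE definition that expressly includes "Events related to the investigational medical device or the comparator". Among its exceptions it then says "Tachyarrhythmia episodes in a patient with ICD /CRT-D indication are not considered as Adverse Events as they are part of his underlying condition". The following sentence takes part of this back: "However, tachyarrhythmia episode have to be reported as Adverse Event in case the episode resulted in a serious medical condition". Recurrent inappropriate therapies of one origin "may be summarized in one Adverse Event Report", which treats them as reportable.

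The opening of Protocol 18 carries the exceptions into the duty to assess and report: "All AEs with exception of those listed in section 18.1 and all DDs of the investigational devices shall be assessed by the investigator".

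Protocol 18.7 lists, among anticipated adverse events, "VT/VF exacerbation" (Tab. 8a, up to 17%), "System- or lead-related arrhythmia" (Tab. 8b, 0.3%) and pacemaker mediated tachycardia (Tab. 8b, frequency not known).

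Outside the AE system, Protocol 8.5.7 asks for IEGMs of event-triggered medical episodes from both groups. For group A therapy and therapy-attempt episodes it also requires an IEGM and a tachyarrhythmia episode form. SAP 17.2 uses that form for the ATP endpoint, with the outcome item "ATP one-shot successfully terminated the episode" coded Yes or No.

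**The concern.** The reason given for the exception fits spontaneous arrhythmia. It does not fit an episode that ATP, a shock, pacing (including MultiPole Pacing) or the lead has induced or accelerated. The wording has no such limit, so it covers both kinds.

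This matters because of what the study is for. Protocol 7.1 sets it up to identify residual risks of the new ICD family and lead. In group A, ATP one-shot is mandatory, as is MultiPole Pacing in CRT-D patients (8.5.4), and Early ATP, which can be delivered before the VF counter is met, is recommended (4.7.5, 8.5.5). Provoked arrhythmia is a plausible harm of such features. Its non-serious cases would be missing from the listing of adverse device effects, and no other planned output asks whether the device caused them.

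**Working it through.** The plan gives no figure on this point to reproduce. The check is a reading of the sections together, followed by a rough scale.

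**1. What the exception covers.** The sentence in 18.1 names tachyarrhythmia episodes in a patient with the study indication, which is every study patient. It sets no condition on cause. The next sentence restores episodes by consequence (a serious condition), again not by cause. What stays exempt is every non-serious episode, provoked or not.

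**2. What follows from exemption.**
- The opening of 18 removes the 18.1 exceptions from investigator assessment, documentation and reporting.
- 18.2 defines an adverse device effect as a kind of AE, and 18.5 defines a SADE as a serious adverse device effect.
- 18.2.1 rates causality for adverse events.

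An episode that is not an AE therefore has no causality rating and cannot become an adverse device effect.

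**3. Conflict inside the Protocol.** The AE definition in 18.1 includes device-related events, and 18.7 lists three kinds of arrhythmia as anticipated adverse events. Under the exception, a non-serious case of any of the three is not an AE.

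**4. What the other records hold.**
- Group A: an IEGM and an episode form for each therapy or therapy attempt, plus the last 3 fast ventricular episodes before a follow-up. 8.5.7 asks the investigator about appropriateness and therapy success.
- Group B: IEGMs are collected, but 8.4.2 specifies no evaluation of them.
- Atrial episodes: IEGMs are collected, but 8.5.7 requires no evaluation.
- SAP 17.2: the listed variables are detection zone, rhythm assessment, ATP programming, first therapy and ATP success. None of these records acceleration or relatedness, so an ATP that merely failed and one that worsened the rhythm are both coded No.

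The episode is usually on file. The causality judgement and the count are missing.

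**5. Primary endpoints.** 18.11 counts only device-related events that are corrected invasively, need invasive correction or cause loss of significant device function. A VT accelerated by ATP and then ended by a shock does not in itself meet this. Serious episodes are restored by 18.1, and 9.8 requires an AE report for every interim intervention. Little effect is expected.

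**6. Scale of the ATP example.** Protocol 7.1.2.1.1 cites an incidence of appropriate ICD therapy of about 10% within 6 months. With 105 group A patients, 0.10 × 105 = 10.5, so roughly 10 patients. Fewer would have an episode in the VF zone with ATP one-shot delivered. If 10 patients were exposed and none had an acceleration, the exact two-sided 95% upper limit would be 1 − 0.025^(1/10) = 0.308, or 31%. Each observed case therefore carries information, and the reporting load is small.

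**7. The one device-specific rate in 18.7.** At the 0.3% of Tab. 8b, 0.003 × 105 = 0.3 patients in group A and 0.003 × 185 = 0.6 in group B. This is a literature rate, and the non-serious share is not stated.

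**The case against.** The best reply is that the text is ambiguous and does not clearly exclude these events. The exception states its own ground, the underlying condition. The definition above it includes device-related events, and 18.7 lists arrhythmias. A sensible investigator could read the exception as covering spontaneous arrhythmia only. That reading is reasonable, but it depends on each investigator, and the sentence as written gives no such limit. The choice should not be left to the site.

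Three stronger readings are tempting, and the documents do not support them.

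- A reader might infer that all tachyarrhythmias are exempt. The next sentence of 18.1 restores those that led to a serious condition, and inappropriate therapies are still treated as AE reports.
- A reader might infer that provoked episodes leave no trace. IEGMs from both groups, the group A form and Home Monitoring data all go to the sponsor, and device deficiencies stay reportable (18.3). Nor can one say that no form records acceleration, because the eCRFs are not among the documents. SAP 17.2 shows only the variables used for one endpoint.
- A reader might apply the 17% of Tab. 8a and arrive at 0.17 × 105 = 17.9 and 0.17 × 185 = 31.5 patients. That figure is a literature maximum for peri-operative events from a 1994 text on defibrillator surgery, and other rows from the same source are tied to thoracotomy or patch leads. It does not measure arrhythmia provoked by ATP, MultiPole Pacing or Plexa. The group A product also exceeds the roughly 10 patients expected to receive appropriate therapy.

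It is also fair to say that an added count in SAP 17 would be descriptive, imprecise and in need of a new form item. That part of the fix is therefore optional.

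**Conclusion.** The concern holds as a defect in a stated reporting rule. As written, 18.1 takes non-serious, device-provoked tachyarrhythmias out of AE and adverse-device-effect classification and out of causality rating, against the AE definition in the same section and the list in 18.7. The loss falls on the descriptive collection of adverse events under 8.4.1 and 8.4.2. It does not fall on the primary tests, where little effect is expected.

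The size cannot be derived from the documents. The figure of roughly 10 of 105 is an expected ceiling on exposure for the ATP example. It assumes that the cited 10% applies to this population, and it says nothing about how many episodes would be provoked. No comparable exposure figure is given for MultiPole Pacing or for the lead in group B. There is also a smaller gap: the serious-condition test in 18.1 is not tied to the seriousness criteria of 18.4, so borderline episodes may be handled differently between sites. The change is worth making because it is cheap and serves the study's stated purpose.

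**What to change.** In Protocol 18.1:

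1. Limit the exception to tachyarrhythmia episodes with no suspected relation to the device, its therapy (ATP, shock), pacing (including MPP), the lead or the procedure.
2. State that episodes suspected to be induced or accelerated by any of these are adverse events and are rated for causality under 18.2.1.
3. Replace the undefined serious-condition test with a reference to the criteria in 18.4.

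Optional: add an acceleration/degeneration item, with its definition, to the episode form that group A investigators already complete. Report the number of episodes and patients descriptively in SAP 17, next to ATP success.

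The cost is a few more AE reports and, if the option is taken, one form item. No new patient procedure is needed. The optional count covers group A only; group B relies on the change to 18.1.

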18.2 Definition of adverse device effects

An adverse device effect (ADE)* is an AE that is related to the use of an investigational medical device. This includes any AE resulting from insufficient or inadequate instructions for use or the deployment, implantation, installation, or operation, or any malfunctioning of the investigational device and any event resulting from use error or from unintentional misuse of the investigational device.

*see ISO14155:2011 3.1

18.2.1 Causality assessment

The relationship between the use of the investigational device (including the medical-surgical procedure) and the occurrence of each adverse event shall be assessed and categorized, considering the presence of confounding factors, such as concomitant medication/treatment, the natural history of the underlying disease, other concurrent illness or risk factors. Each SAE will be classified according to five different levels of causality. Based on MEDDEV 2.7/3 rev 3, the investigator will use the following categories to assess the relationship of the serious adverse event to the investigational medical device or procedures and the sponsor will review the investigator's categorization:

Not related: the relationship to the device or procedures can be excluded

Unlikely: the relationship with the use of the device seems not relevant and/or the event can be reasonably explained by another cause, but additional information may be obtained.

Possible: the relationship with the use of the investigational device is weak but cannot be ruled out completely. Alternative causes are also possible (e.g. an underlying or concurrent illness/ clinical condition or/and an effect of another device, drug or treatment). Cases where relatedness cannot be assessed or no information has been obtained should also be classified as possible.

Probable: the relationship with the use of the investigational device seems relevant and/or the event cannot reasonably be explained by another cause, but additional information may be obtained.

Causal relationship: Causal relationship: the serious event is associated with the investigational device or with procedures beyond reasonable doubt.

The investigators will distinguish between the serious adverse events related to the investigational device and those related to the device procedures (i.e. procedure related to the application of the investigational medical device only and therefore not to any other procedure for other devices or treatments applied later throughout the clinical investigation, for instance to treat adverse events). Replacement procedures of the investigational device are considered as an application of a new investigational device and shall be assessed accordingly. The sponsor will review the investigator's assessment of device or procedure relatedness.

An adverse event can be related both to procedures and the investigational device. Complications of procedures are considered not related if the said procedures would have been applied to the patients also in the absence of investigational device use or application. For example, in the ICD arm of this clinical investigation, a cardiac perforation with the right ventricular event will not be considered as related to the procedure of investigational device use since the right ventricular lead is not specific for the use of the investigational device.

